## 2) Safety indicators

① Blood glucose and lipids: tested on days 3 and 13 of the test;

② Blood count: tested on day 3 and 26 of the trial;

③ Anxiety: to evaluate the mood changes after intervention with GAD-7.

tested on day 13 of the trial.

④ Adverse reaction records: allergy, gastrointestinal discomfort during the trial.

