## **2. Study design**

This study intends to use a randomized controlled trial design to vaccinate all participants against rabies and perform ARA interventions during vaccination.

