## **3. Study objectives:**

The objectives of this study are:

- 1) to test the ARA intervention on promoting rabies vaccination efficacy;
- 2) to evaluate the safety of using ARA intervention;
- 3) to explore the potential mechanism

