### **Drop out**

- 1) Use of other nutritional supplements during the intervention;
- 2) Those who do not consume nutritional supplements as prescribed by the doctor
- 3) Those who develop a major illness;
- 4) Those who experience severe vaccine allergy;
- 5) Voluntary withdrawal.

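### The only clinical-event record in the safety indicators names allergy and gastrointestinal discomfort, leaving non-allergic vaccine reactions and major illness without a stated place

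*Protocol*

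**What the plan says.** Protocol section 3 lists as its second objective "to evaluate the safety of using ARA intervention". The Safety indicators list in section 4.4 carries that objective through four items:

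- "Blood glucose and lipids: tested on days 3 and 13 of the test"
- "Blood count: tested on day 3 and 26 of the trial"
- "Anxiety: to evaluate the mood changes after intervention with GAD-7", done on Day 13
- "Adverse reaction records: allergy, gastrointestinal discomfort during the trial"

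The Drop out list in section 4.1 includes "Those who develop a major illness" and "Those who experience severe vaccine allergy". It does not say whether either is also a safety outcome. Section 2 states that the trial will "vaccinate all participants against rabies and perform ARA interventions during vaccination", so the supplement and the vaccine overlap in time. Section 1 gives ARA's immunomodulatory effect, and its possible ability to improve vaccination, as the reason for testing it.

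**The concern.** A safety objective can be met only for events that someone is told to write down. The fourth safety indicator is the one place where the protocol tells staff which clinical events to record, and it names two kinds. There is no general adverse-event category and no serious adverse-event category anywhere in the document.

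Two kinds of event matter here. The first is the non-allergic reaction to the vaccine: fever, headache, pain or swelling at the injection site. Every participant is vaccinated, so these can occur in every arm, and a supplement chosen to act on the immune response could plausibly change how often or how strongly they occur. They therefore bear on the safety of ARA, even though vaccine safety is not an objective in its own right. The second is major illness, which the protocol foresees but mentions only as a route out of the study. If these events are not collected, an analysis plan written later cannot recover them.

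**Working it through.** The protocol states no safety figure to recompute, so the main check is to take each kind of event and ask where the protocol places it.

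- **Allergic reaction to the capsules or to the vaccine.** The word allergy in the fourth safety indicator is not tied to the supplement, so both fit.
- **Severe vaccine allergy.** It fits the same indicator and is also a drop-out reason. The two lists are compatible but not linked.
- **Gastrointestinal discomfort.** Named.
- **Fever, headache, injection-site reaction, infection.** Not named. Glucose, lipids and blood count are laboratory values taken on two days each, and GAD-7 is an anxiety score taken on Day 13. None of them is an event record, so none would log a reaction occurring between visits. The cytokines are a secondary indicator and are not an event record either.
- **Major illness.** Named under Drop out, absent from Safety indicators.

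On wording, the list of baseline items under Baseline Investigation is explicitly left open at its end. The adverse reaction item is not. This favours reading it as a complete list but does not prove it.

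For scale, only the group size in section 4.2 is available. It reproduces:

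- N = 2 × ((1.96 + 1.2816) × 778.4 / 1158.2)² = 9.49, rounded up to 10.
- With 20% loss, 10 / 0.8 = 12.5, rounded up to 13 per group.

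One event in an arm of 13 is 1/13 = 7.7%. The documents give no event rates, so the rates below are assumptions. The chance of at least one event in an arm of 13 is 1 − (1 − p)^13:

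- p = 1%: 12%
- p = 5%: 49%
- p = 10%: 75%
- p = 20%: 94.5%

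A reaction as common as 10% to 20% would probably appear in every arm. Under a literal reading of the list, it would have no line on the form.

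On cost, the Biological sample collection section sets contacts on Days 3, 6, 13, 16, 19 and 26. That is six occasions on which events could be asked about without adding a visit.

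**The case against.** The strongest reply is that this reads a terse line too strictly. The protocol is short and loosely worded, the item does not say that only these two events count, and nothing tells staff to ignore others. The two terms could simply be the reactions expected from oil capsules. That is fair. It means the omission of other events is an inference about how sites would act. It also means that sites could act differently from one another, which is itself a reason to settle the wording.

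A reader might infer that vaccine reactions as a whole go unrecorded. The text does not support that: allergic reactions to the vaccine, including severe ones, fall within the recorded category. A reader might also infer that a participant with a major illness leaves without being counted by arm. The Drop out list does not say so. Applying the rule requires the illness to be identified, and the protocol is silent on whether it then enters the safety data. Tabulating drop-out reasons is also ordinary analysis-plan material. What remains is that the protocol assigns the event no safety role.

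It can be added that the objective concerns ARA and not the vaccine, and that a link between ARA and stronger vaccine reactions is a hypothesis the documents do not state. Both are true. But the supplement is given around vaccination for its effect on immunity, and the protocol itself plans to look for cytokine changes caused by it, so the hypothesis is a reasonable one to be able to examine.

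Last, 13 per arm gives little power for comparing event counts, however complete the form. That also stands. With no events among 13 participants, the one-sided 95% upper limit is still 1 − 0.05^(1/13) = 20.6%. The safety comparison will be descriptive, and a descriptive comparison depends most on complete recording.

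**Conclusion.** The point holds in a limited form. The only clinical-event record among the four safety indicators names two kinds of reaction. Non-allergic vaccine reactions and the major illness listed under Drop out have no stated place among those indicators. Followed as written, the safety comparison would miss them.

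This rests on two assumptions: that sites record what the protocol names and little else, and that no separate case report form already asks for more. It does not show that safety is assessed by two items alone, since laboratory values and GAD-7 are also measured. Nor does it show that any event is deliberately excluded. The protocol does not commit itself to a conclusion of no safety difference.

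The number of events at stake cannot be calculated from the document. The point is worth acting on because it concerns what is collected for a stated objective and the remedy is cheap. It does not affect the antibody outcomes or the sample size.

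**What to change.** In the Safety indicators list, replace the adverse reaction item with a record of all adverse events, by arm, from the first capsule to the last study visit. Include non-allergic local and systemic reactions after each vaccine dose given in the trial. Keep allergy and gastrointestinal discomfort as items asked about specifically.

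Reconcile the Drop out list with the Safety indicators list, so that a major illness or severe allergy leading to drop-out is also counted as a safety outcome in the participant's arm. This concerns recording only and leaves the drop-out rules as they are.

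Two details of the window need stating:

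- **Start.** Capsules begin on Day 3 or Day 6 depending on the group. The period to Day 26 is therefore 26 − 3 = 23 days or 26 − 6 = 20 days, and the tables should show this.
- **End.** The last visit is vaccination Day 20, whereas section 1 describes a programme with a dose on Day 21. The protocol does not say whether that dose is part of the trial. If it is, the recording window and the vaccine schedule must be reconciled.

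The cost is a broader form at the six existing contacts and slightly more tabulation. No visit, sample or procedure is added.

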### **Biological sample collection (6 times in total):**

Test Day 3: venous fasting blood collection of 30 ml and feces of 10 g;

Trial Day 6 (vaccination Day 0): 5 ml of blood collected intravenously; 10 g of feces;

Trial Day 13 (vaccination Day 7): 5 ml of blood collected intravenously on an empty stomach; 10 g of feces;

Trial Day 16 (vaccination Day 10): 5 ml of blood collected intravenously; 10 g of feces;

Trial Day 19 (vaccination Day 13): 30 ml of blood collected intravenously; 10 g of feces;

Trial Day 26 (vaccination Day 20): 5 ml of blood collected intravenously; 10 g of feces.

Preservation of serum, plasma and whole blood: frozen at -80°C after sampling.

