###### **2) Secondary indicators**

- ① Serum blood fatty acid profiles: to reflect the change of fatty acid profiles after intervention. Will be tested on day 6, 13, 16 and 19.

- ② Cytokines: to test the potential blood cytokines changes triggered by ARA supplementation. Will be tested on day 6, 13, 16, 19 and 26

- ③ Feces microbiota: the microbiota in feces samples will be examined with metagenome to explore the potential gut-immune response caused by intervention. Will be tested on Day 3, 6, 13, 16, 19 and 26 of the study.

- ④ Blood metabolites: To examine the metabolites changes in blood after intervention.

Will be tested on Day 6, 13 and 16 .

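### Fasting is required at only one of the days on which serum fatty acids and blood metabolites are measured (Day 13), so within-arm change can mix supplement effect with meal state, and between-arm comparisons lose precision

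*Protocol*

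**What the plan says.** Protocol section 4.4, under Biological sample collection, lists six draws. Two carry a fasting condition:

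- Day 3: "Test Day 3: venous fasting blood collection of 30 ml and feces of 10 g"
- Day 13: "Trial Day 13 (vaccination Day 7): 5 ml of blood collected intravenously on an empty stomach; 10 g of feces"

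The other draws used for the two assays carry none:

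- Day 6: "Trial Day 6 (vaccination Day 0): 5 ml of blood collected intravenously; 10 g of feces"
- Day 16: "Trial Day 16 (vaccination Day 10): 5 ml of blood collected intravenously; 10 g of feces"
- Day 19: "Trial Day 19 (vaccination Day 13): 30 ml of blood collected intravenously; 10 g of feces"

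Under Secondary indicators, the serum fatty acid profile is there "to reflect the change of fatty acid profiles after intervention. Will be tested on day 6, 13, 16 and 19". The purpose of the metabolite panel is given as "To examine the metabolites changes in blood after intervention", with tests on Days 6, 13 and 16. Under Safety indicators, blood glucose and lipids are tested on Days 3 and 13, the same two days that require fasting.

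**The concern.** Both assays are defined by change over time, yet the sampling condition is not held constant over time. The fasting days coincide with the glucose and lipid days, which suggests that fasting was set for those safety tests and not with the biomarker series in mind.

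A serum fatty acid profile or metabolite panel can be expected to respond to a recent meal and, while supplements are being taken, to recently swallowed oil. The single fasting-required point falls at about the end of supplementation, where the exposure biomarker would be expected to be highest. A rise from Day 6 to Day 13, or a fall from Day 13 to Days 16 and 19, read within one arm could therefore be partly a change of meal state, or be masked by one.

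These series are the trial's evidence that ARA reached the blood, and they support its third objective, on mechanism. Analysis can address meal state only if meal times are recorded, and the Protocol mentions no such record.

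**Working it through.** **1. Sampling condition against assay days** (section 4.4)

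| Trial day | Fasting required? | Fatty acids | Metabolites | Glucose and lipids |
|---|---|---|---|---|
| 3 | Yes | – | – | Yes |
| 6 | Not stated | Yes | Yes | – |
| 13 | Yes | Yes | Yes | Yes |
| 16 | Not stated | Yes | Yes | – |
| 19 | Not stated | Yes | – | – |

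Fasting is required on 1 of 4 fatty acid days and 1 of 3 metabolite days. The changes that involve Day 13 are 6–13, 13–16 and 13–19 for fatty acids, and 6–13 and 13–16 for metabolites. In all five, one end has a fasting requirement and the other does not.

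**2. Where Day 13 sits.** Section 4.3 runs the supplement up to the second vaccine dose. The Background gives a schedule of Days 0, 7 and 21, and the sampling list equates trial Day 13 with vaccination Day 7. Supplementation therefore ends at about trial Day 13, and no capsules are due on Days 16 and 19.

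**3. Arm size.** The only figure the Protocol computes is its sample size (section 4.2), which sets the arm size used here. It reproduces:

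- pooled SD = √((1093.9² + 123.4²)/2) = 778.4
- difference = 1323 − 164.8 = 1158.2
- n = 2 × ((1.960 + 1.282) × 778.4/1158.2)² = 9.49, rounded up to 10
- with 20% loss, 10/0.8 = 12.5, rounded up to 13

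That calculation concerns neutralizing antibody and is not in dispute.

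**4. Bias.** Illustration with assumed values: a true ARA effect of +1 unit on the Day 6 to Day 13 change, and a fed-to-fasting shift of −1 unit common to all arms.

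- Within the ARA arm: 1 − 1 = 0
- Within placebo: 0 − 1 = −1
- ARA minus placebo: 0 − (−1) = 1

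The within-arm change is wrong by the full shift. The between-arm difference in change is right.

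**5. Precision.** Let the within-person variance be s² at the fasting point and s²(1 + k) at the unfasted point. The variance of the change is s²(2 + k), against 2s² if both points are fasting. The SD ratio is √((2 + k)/2).

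- k = 0.5: √1.25 = 1.118, a 12% rise
- k = 1.0: √1.5 = 1.225, a 22% rise

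In terms of numbers, 10 per arm then give the precision of 10/1.25 = 8 or 10/1.5 = 6.7 per arm for that contrast. The Protocol gives no value for k, so the 50% to 100% range is an assumption.

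**The case against.** A reader might infer that participants are fed on Days 6, 16 and 19, and that every ARA effect involving Day 13 is confounded with fasting. The Protocol supports neither reading.

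- **Silence is not a fed state.** For Days 6, 16 and 19 the list says only that blood is taken from a vein. Staff may in practice draw fasting blood at every visit. What stands is that the list requires it on some days and not on others.
- **The placebo arm protects the main comparison.** One sampling list covers all arms, so a common meal-state shift cancels between ARA and placebo, both on a given day and in change, as step 4 shows. What remains is lost precision, and bias only if meal state differs by arm or interacts with ARA.
- **Capsules are not an issue after Day 13.** On the Protocol's own timeline, Days 16 and 19 can carry meal variation only.

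One exception to the cancellation stands. On Day 6 the Day 3 ARA arm is already supplemented, the Day 6 ARA arm is just starting, and placebo is a different oil (sunflower). If a capsule precedes an unfasted draw that day, the recently absorbed oil could differ by arm, and a between-arm fatty acid contrast could then be biased.

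Two limits also stand. Uniform fasting does not turn Day 6 to Day 13 into a before-and-after change in the Day 3 ARA arm, because that arm has had three days of supplement by Day 6 and neither assay is done on Day 3. And the primary antibody outcomes are not touched by this point.

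**Conclusion.** The point holds as an inconsistency in sampling conditions for two secondary measures. Day 13 is the only fasting-required point in either series, so five changes (three for fatty acids, two for metabolites) can mix supplement effect and meal state when read within an arm. The counts and the mismatch rest on the Protocol's text alone.

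Randomized ARA-versus-placebo comparisons are not biased by a shift common to the arms, but they carry avoidable noise in arms of 10 to 13. The 12% to 22% increase in the SD of a Day 6 to Day 13 change is correct arithmetic that rests wholly on the assumed extra variance. The Day 6 capsule effect is a possibility that the Protocol leaves open, not a demonstrated bias.

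The change is worth making because it is cheap and the affected series are the basis of the mechanism objective.

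**What to change.** In section 4.4, Biological sample collection:

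- Require fasting, as on Day 13, for the Day 6 and Day 16 draws (both assays) and for the Day 19 draw (fatty acids).
- Take the Day 6 and Day 13 draws before any capsules due that day.
- Record time since last meal and time since last capsule at each draw.
- Keep samples that turn out not to be fasting, and use the recorded times in a sensitivity analysis. Discarding them would lose post-randomization data in small arms and could make the missing data selective.

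The cost is an overnight fast before three visits that are already planned, plus two recorded times per draw. No extra visit, blood volume or assay is needed.
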